**STUDY-WIDE NUMBER OF PARTICIPANTS:**

The total number of participants to be accrued with OASIS is 160.

**STUDY-WIDE RECRUITMENT METHODS:** N/A

**MULTI-SITE RESEARCH:** N/A

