**PROCEDURES INVOLVED:**

Prospective, double-blinded, randomized clinical trial.

Randomization: Patients will be approached after repair of OASIS has been completed, and prior to the epidural catheter removal. After informed consent, eligible patients will be randomized to 1 of 3 possible paired interventions:

- 1) Epidural saline + intravenous saline
- 2) Epidural morphine 3mg + intravenous saline
- 3) Epidural morphine 3mg + intravenous ketamine 0.3mg/kg (based on pre-delivery weight)

The subjects will be randomized to a 1/5 chance for group 1 and a 2/5 chance for group 2 and group 3. Randomization and study drug preparation will be conducted by the pharmacy on Prentice 10th floor. The epidural catheter will be removed after study drug or placebo administration, and the patient will be transferred to postpartum unit following standard institutional protocol.

Post-neuraxial morphine order set will be ordered for postpartum analgesia and monitoring.

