#### **DATA AND SPECIMEN BANKING: N/A**

#### **DATA AND SPECIMEN MANAGEMENT:**

The primary outcome of this study is the proportion of women with pain (VRS > 4, on a 0 to 10 scale) with activity at 7±3 days postpartum. Based on the study of Macarthur et.al evaluating pain following perineal injury following childbirth, we estimated that 55% of women would have pain (VRS > 4, on a 0 to 10 scale) at 7 days. We assumed an absolute reduction of 25% in pain in women receiving epidural morphine 3mg + intravenous saline compared to epidural saline +

intravenous saline, and an absolute reduction of 30% in pain in women receiving epidural morphine 3mg + intravenous ketamine 0.3 mg/kg compared to epidural saline + intravenous saline. Groups sizes of 30:60:60 will be required to detect a difference in an effect size of 0.25 (Cramér's  $\omega$ ) at a power of 0.8 and an alpha of 0.05 using  $\chi^2$  statistic. A sample of 150 subjects will be randomized using a 1:2:2 randomization to epidural saline plus intravenous saline, epidural morphine + intravenous saline, and epidural morphine + intravenous ketamine groups. We will recruit up to 160 patients to account for subjects that decline participation and lost to follow-up.

The completed data forms will be kept in folders with only the study ID number as an identifier. These folders will be placed in a secure, locked cabinet in the Office of the Section of Obstetrical Anesthesiology located in Prentice Women's Hospital 9th floor. REDcap will be used for data entry. Only study team members will have access to the data files. Data will be password protected using a Department of Anesthesiology dedicated computer which is backed up nightly by the departmental server which is located on the 5th floor Arkes Pavilion. The access is controlled by key card and password protected by the departmental data manager.

Only the study ID number will be used to identify participants during data analysis. The data will be stored in the departmental computer until the completion of the study, including the final data analysis. Members of the anesthesia team collecting these data will be educated on the process prior to approaching prospective participants. Data both electronic and paper will be destroyed 5 years after the study has been completed using current standards and vendors.

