**NUMBER OF LOCAL PARTICIPANTS:**

The total number of participants to be accrued is 160.

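### The number to be randomized equals the number required for analysis (150), and the 10 extra places are shared between women who decline and women lost to follow-up, so the allowance for loss is at most 6.25% and may be nil

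*Combined protocol and SAP*

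**What the plan says.** Three statements in the sample-size paragraph of DATA AND SPECIMEN MANAGEMENT bear on this.

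- The requirement: "Groups sizes of 30:60:60 will be required to detect a difference in an effect size of 0.25", "at a power of 0.8 and an alpha of 0.05 using" a chi-square test. That is 150 women.
- The number randomized: "A sample of 150 subjects will be randomized using a 1:2:2 randomization".
- The margin: "We will recruit up to 160 patients to account for subjects that decline participation and lost to follow-up".

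STUDY-WIDE NUMBER OF PARTICIPANTS says "The total number of participants to be accrued with OASIS is 160", and NUMBER OF LOCAL PARTICIPANTS says "The total number of participants to be accrued is 160". Neither says how many of the 160 are randomized.

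PROCEDURES INVOLVED fixes the order of events: "After informed consent, eligible patients will be randomized to 1 of 3 possible paired interventions". The primary outcome is pain "with activity at 7±3 days postpartum", so it is measured after randomization. STUDY TIMELINES mentions loss to follow-up as a planning factor, but no section gives a rate.

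**The concern.** A power calculation gives the number of women whose outcome must be analysed. The number randomized should exceed it by the expected loss. Here the two are equal, and the only allowance is 10 further places that also have to cover women who decline. Those two groups lie on opposite sides of randomization. A refusal at consent costs recruitment effort but no analysed outcome. A woman lost after randomization costs an outcome, and only another randomized woman can make that up.

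The practical question is where the randomization table ends. DRUGS OR DEVICES says the pharmacy and the departmental data manager hold it. A team that follows the sentence on randomization stops at 150; a team that follows the accrual figure may go to 160. At stake is the power of the primary comparison, which has no slack even with complete data.

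**Working it through.** **Inputs from the documents.** Required 30 + 60 + 60 = 150; effect size w = 0.25; alpha 0.05; power 0.80; chi-square test; allocation 1:2:2; ceiling 160; assumed pain rates 55%, 55 − 25 = 30% and 55 − 30 = 25%. Three arms and a yes/no outcome give 2 degrees of freedom; this is inferred, not stated. **Assumed here:** loss rates up to 20%, because the plan gives none.

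**Step 1. Reproduce the plan's figure.** Power = P(noncentral chi-square with 2 df and noncentrality N × w² exceeds 5.99). With w = 0.25, power 0.80 needs N = 154.2. At N = 150 the noncentrality is 150 × 0.0625 = 9.375 and power is 0.788. This is close to the stated 150 and 0.80, though slightly short.

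**Step 2. Size of the margin.** 160 − 150 = 10, and 10/160 = 6.25%. This is the largest loss that still leaves 150, and only if all 160 are randomized. With k decliners counted in the 160, 160 − k are randomized and 10 − k losses can be absorbed.

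**Step 3. Power under the two readings, at w = 0.25.**

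| Loss (assumed) | 150 randomized: analysed, power | 160 randomized: analysed, power |
|---|---|---|
| 0% | 150, 0.788 | 160, 0.815 |
| 6.25% | 140.6, 0.760 | 150, 0.788 |
| 10% | 135, 0.742 | 144, 0.771 |
| 20% | 120, 0.688 | 128, 0.718 |

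**Step 4. Number to randomize to keep 150 evaluable.** 150/(1 − loss), rounded up: 154 at 2%, 158 at 5%, 160 at 6.25%, 167 at 10%, 177 at 15%, 188 at 20%. Any loss above 6.25% needs more than 160.

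**Step 5. A separate matter that must not be mixed in.** The plan's own rates do not give w = 0.25. The weighted mean rate is 0.2 × 0.55 + 0.4 × 0.30 + 0.4 × 0.25 = 0.33. Then w² = [0.2 × 0.22² + 0.4 × 0.03² + 0.4 × 0.08²]/(0.33 × 0.67) = 0.0126/0.2211 = 0.0570, so w = 0.239. At that effect size power is 0.748 with 150 evaluable and no loss at all, and 0.699 at 135. Of the fall from 0.80 to about 0.70 at 10% loss, roughly half therefore comes from the effect size and half from attrition.

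**The case against.** A reader might infer that any loss must leave the trial with fewer than 150 outcomes. The documents do not establish that. It holds only if exactly 150 are randomized and none is replaced. The margin sentence gives loss to follow-up as one reason for going up to 160, which makes sense only if some women beyond 150 are randomized, and two other sections give 160 as the number accrued. Read together, 150 may be the target and 160 the ceiling, with up to 10 losses absorbed. That stands, and it limits the point to an inconsistent allowance.

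The reference to declining may also cover women who agree and then drop out, since WITHDRAWAL OF PARTICIPANTS permits that at any time. The text does not say. If that was meant, it should be written, because such women belong with the losses.

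High attrition should not be presumed either. INCLUSION AND EXCLUSION CRITERIA requires willingness to attend either the obstetrician's office or the perineal clinic in the first week, and ECONOMIC BURDEN TO PARTICIPANTS describes the first-week visit as standard care. These features make a low loss plausible, but they do not supply a rate. On the other side, the withdrawal section lets a woman have all her data removed on request.

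Finally, randomizing 160 does not restore 0.80 at every loss rate. That is correct: at w = 0.25 it needs about 155 evaluable women, so 160 can lose only 5 (5/160 = 3.1%). The gain is a clear allowance and an honest power figure.

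**Conclusion.** The concern holds in this limited form. The required number and the number randomized are both 150, the margin of 10 is assigned to two groups of which only one can use it, and no loss rate is stated. The allowance for loss is therefore between nil (150 randomized, no replacement) and 6.25% (all 160 randomized, no decliners counted).

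At the plan's w = 0.25, an assumed 10% loss gives power of 0.742 or 0.771 according to the reading, against 0.788 with 150 evaluable; an assumed 20% loss gives 0.688 or 0.718. These figures rest on a 2-df chi-square test and on loss rates chosen here. The effect is modest at 10%, but the plan has no reserve to absorb it. The further drop to 0.748 at 150, from the stated rates giving w = 0.239, is a different point and should be settled separately.

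**What to change.** In the sample-size paragraph:

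1. State that 160 women will be randomized, 32:64:64, which keeps 1:2:2.
2. State that women who decline before randomization do not count toward the 160, and that the 10 extra are for loss to follow-up only.
3. State the assumed loss rate and its basis.
4. Replace the power of 0.80 with the power at the resulting evaluable number, for example 0.788 at 6.25% loss, 0.771 at 10% or 0.718 at 20% with w = 0.25. If the effect size is recalculated from the stated rates, use w = 0.239 throughout instead.

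Use the same wording in the two sections that give the accrual number. The cost is a text change, a randomization table of 160 entries and a slightly less favourable stated power. No accrual beyond the stated 160 is needed. If the expected loss exceeds 6.25% and the team wants to keep 150 evaluable, it would need more than 160 (167 at 10%), which would require raising the approved accrual.

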#### **PROVISIONS TO MONITOR THE DATA TO ENSURE THE SAFETY OF PARTICIPANTS:**

A data safety monitoring board consisting of the Department of Anesthesiology Director of Research, a Urology/Gynecology faculty member, and a statistician along with the study research personnel will periodically evaluate the data collected to determine whether participants remain safe. Safety data and adverse event data will be reviewed using the medical record and data collection form. It will be reviewed every 50 subjects or if one of the study subject experiences a rapid response team intervention and review. Data will be compared between groups using the  $\chi^2$  statistic or the Fisher's exact test. A  $P < 0.05$  will be required to reject the null hypothesis.

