#### **DRUGS OR DEVICES:**

The study drugs are FDA approved. The departmental data manager and the 10th floor pharmacy Prenticed Women's Hospital will have the randomization table. The study drugs will be prepared and dispensed by the 10th floor pharmacy, and administered by a physician. The anesthesiologist, nurses and study research personnel will be blinded to the study group.

The MEDoc pathway device is owned by Northwestern University and has been tested and stickered by Biomedical Engineering at Northwestern Hospital. The device is stored in Arkes Pavilion on the 10th floor Department of Anesthesiology Administrative suite in a locked research closet.

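### Study research personnel are to be blinded, yet the monitoring plan has them take part in reviews every 50 subjects in which data are compared between groups

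*Combined protocol and SAP*

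**What the plan says.** Under Procedures Involved, the design is described as "Prospective, double-blinded, randomized clinical trial". Under Drugs or Devices, the randomization table is held by the departmental data manager and the pharmacy, and "The anesthesiologist, nurses and study research personnel will be blinded to the study group".

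The section on monitoring data for participant safety sets up a board with three named kinds of member: the anesthesiology department's director of research, someone from the urology/gynecology faculty, and a statistician. The clause that matters reads: "a statistician along with the study research personnel will periodically evaluate the data collected to determine whether participants remain safe". It continues: "Safety data and adverse event data will be reviewed using the medical record and data collection form". On timing: "It will be reviewed every 50 subjects or if one of the study subject experiences a rapid response team intervention and review". On method: "Data will be compared between groups using the" chi-square or Fisher's exact test, and P < 0.05 "will be required to reject the null hypothesis".

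The section does not say whether groups are coded, whether part of the meeting is closed to study staff, or what follows if P falls below 0.05.

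**The concern.** One named set of people is blinded in one section and evaluates by-group data in another. Both statements cannot be followed as written.

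The primary outcome is a patient's own verbal pain rating, collected within about a week of delivery. The anesthesia research team recruits (Recruitment Methods), and research nurses in the section help with recruitment and follow-up (Resources Available). Staff who know how the arms are trending can, without intending it, alter how they present the trial, pursue follow-up or elicit a pain score. That cannot be undone at analysis.

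A secondary concern is the P < 0.05 criterion at each review. It has no stated consequence, and with groups this small it says little about uncommon harm.

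**Working it through.** **1. The blinding conflict (no arithmetic needed)**

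- Drugs or Devices: study research personnel do not know the group.
- Monitoring section: study research personnel evaluate the data with the board, and the data are compared between groups.
- No procedure in either section reconciles the two.

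**2. Would coded labels be enough?**

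Allocation is 1/5, 2/5, 2/5 (Procedures Involved), and the sample size paragraph confirms it: "Groups sizes of 30:60:60 will be required". At 50 subjects the expected sizes are 50 × 1/5 = 10, 50 × 2/5 = 20 and 50 × 2/5 = 20. Any by-group table with denominators near 10, 20 and 20 identifies placebo. The two active arms would be separated only if their side-effect profiles differ visibly.

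**3. How much of the trial is exposed?**

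Of the planned 150, 150 − 50 = 100 (two thirds) are still to be enrolled after the first review, and 150 − 100 = 50 (one third) after the second. The third review coincides with the planned sample. Follow-up runs to 12 months.

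**4. The P < 0.05 criterion (secondary)**

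The monitoring section gives no operating characteristic to reproduce. The documents give no adverse event rates, so every rate below is an assumption.

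*Smallest significant count, two-sided Fisher, placebo versus one active arm, no placebo events.* At 50 subjects with 8 events in total, the probability that all fall in the active arm is C(20,8)/C(30,8) = 125970/5852925 = 0.0215. The equally or less likely tables in the other tail (6, 7 or 8 events on placebo) add 0.0072, so P = 0.029. With 7 events P = 0.064. The same calculation at later reviews gives:

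| Subjects | Placebo | Active arm needed | P |
|---|---|---|---|
| 50 | 0/10 | 8/20 (40%) | 0.029 |
| 100 | 0/20 | 8/40 (20%) | 0.043 |
| 150 | 0/30 | 8/60 (13%) | 0.048 |

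*Chance of P < 0.05 at each review if the true placebo rate is 0%.* This is P(X ≥ 8) with X binomial(n, p), and n = 20, 40 or 60.

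| Assumed active rate | 50 | 100 | 150 |
|---|---|---|---|
| 5% | <0.1% | 0.1% | 1.0% |
| 10% | 0.04% | 4.2% | 24.8% |
| 20% | 3% | 56% | 93% |

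For a common harm with a large difference, assumed 20% versus 60%, simulation gives about 97% over the three reviews.

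*False positives over three unadjusted reviews, per event type, by simulation.* Fisher (placebo versus one active arm) gives about 1% at a 2% event rate, 3% at 5%, 5% at 10%, 7% at 20% and 8% at 40%. The 3×2 chi-square gives 8.0% at a 5% event rate, 9.6% at 10%, 11.0% at 30% and 10.7% at 50%.

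**The case against.** **On the blinding conflict.** A grouped comparison need not unblind any one patient. The randomization table stays with the data manager and the pharmacy, so the next assignment remains concealed. The documents do not say that the staff at the reviews are the ones who record the clinic pain score. Staff also collect sedation and drug-effect scores directly after dosing, so some unblinding could occur without any review. The comparison sentence might even be a general analysis statement, since the protocol has no separate analysis section. These points limit the claim to arm-level knowledge and a possible, not demonstrated, bias. They do not remove the contradiction: the comparison sentence directly follows the review schedule, and no masking is described.

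**Stronger readings that a reader might infer, and that the documents do not support:**

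- *The board would wait for P < 0.05 before acting.* No stopping, continuing or waiting is tied to that threshold, and a single rapid response event triggers a review without any P value.
- *The reviews cannot detect plausible harm.* That depends wholly on assumed rates. At 0% versus 20% the chance is 93% at 150 subjects. Low power for rare events is a limit of the sample size under any method, and exact intervals would also be wide at 10 versus 20.
- *Repeated looks inflate the primary outcome's alpha.* The section names safety and adverse event data. The looser phrase about the data collected leaves a gap worth closing, but no interim efficacy test is planned.
- *Repeated safety testing gives about 11% false positives.* That holds for the chi-square at common event rates. With Fisher's test and uncommon events the rate stays at or below 5%. An unadjusted threshold for harm also errs towards caution.

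**Conclusion.** The blinding conflict is real and carries the point. Following the monitoring section as written would show arm-level results to people whom the protocol says are blinded, with up to two thirds of the planned sample still to be recruited and a self-reported primary outcome. It should be corrected before any review takes place. The conclusion rests on the text alone, plus the assumption that group sizes follow the planned 1:2:2 ratio closely enough to identify placebo. It does not claim that individual allocations are revealed or that bias has been shown.

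The P < 0.05 criterion is a minor matter. It has no linked action, almost no power for rare or uncommon harm, and little power at the first review. Under assumed true rates of 0% versus 5%, 10% and 20%, the chance of P < 0.05 at 150 subjects is about 1%, 25% and 93%.

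**What to change.** Amend the monitoring section as follows.

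1. Only the three named non-study members (director of research, urology/gynecology member, statistician) see by-arm data. The data manager, who already holds the randomization table, prepares the report. Study research personnel receive pooled data only.
2. State that no efficacy outcome is compared between groups at these reviews.
3. Replace the P < 0.05 requirement with by-arm event counts and risk differences with exact confidence intervals, judged by the board.

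The cost is a few sentences, with no new members, patients or visits. The one real downside is that study personnel lose access to by-arm data until the trial ends. The intervals will be wide at the first review, but they show that uncertainty openly, where a non-significant P value could be read as reassurance.

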III  Information will be collected remotely via electronic and/or printed surveys, depending on the patient's preference	6 weeks	
 
- Perineal pain scores (VRS)
 
-Need for additional analgesic intake for management of perineal pain (yes or no) 
 
• Total analgesic consumption (opiates/nsaids)
 
 
 
-McGill Pain Questionnaire
 
-Brief Pain Inventory (BPI) Short Form
 
- If plan was to breastfeed, is patient currently breastfeeding? yes or no? If not, why did she stop?
 
-Edinburgh Postnatal Depression Scale (EPDS)
 
-Maternal Postnatal Attachment Scale (MPAS)
 
-Patient Reported Outcome Measurement Information System (PROMIS) 29
 
	
IV	3 months	-Perineal pain score (VRS)	

Information will be collected remotely via electronic and/or printed surveys, depending on the patient's preference		
 
-Need for additional analgesic intake for management of perineal pain (yes or no) 
 
• Total analgesic consumption (opiates/nsaids)
 
 
 
-Physical therapy treatment (yes or no)
 
-The McGill Pain Questionnaire
 
-Brief Pain Inventory (BPI) Short Form
 
- If plan was to breastfeed, is patient currently breastfeeding? yes or no? If not, why did she stop?
 
-Edinburgh Postnatal Depression Scale (EPDS)
 
-Maternal Postnatal Attachment Scale (MPAS)
 
-Patient Reported Outcome Measurement Information System (PROMIS) 29
 
- Female Sexual Function Index (FSFI)
 
	
V	6 Months	
 
-Perineal pain score (VRS)
 
-Physical therapy treatment for pelvic pain (yes or no)
 
- If plan was to breastfeed, is patient currently breastfeeding? yes or no? If not, why did she stop? -
 
Patient Reported Outcome Measurement Information System (PROMIS) 29
 
- Female Sexual Function Index (FSFI)
 
	
VI	12 Months	
 
-Perineal pain score (VRS)
 
-Physical therapy treatment for pelvic pain(yes or no)
 
- If plan was to breastfeed, is patient currently breastfeeding? yes or no? If not, why did she stop?
 
	

		-Patient Reported Outcome Measurement Information System (PROMIS) 29 - Female Sexual Function Index (FSFI)	
--	--	---	--

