Phase I will involve the collection of data points from patient interview, chart review, and surveys during the initial hospitalization. Phase II entails the administration of a brief questionnaire and surveys to the patient during their 1 week follow up appointment in the specialty perineal clinic.

Thermal pain test (threshold measurement) will be performed during the first follow up visit if the subject attends the the PEAPOD clinic. The Medoc PATHWAY Pain & Sensory Evaluation System (Medoc Ltd, Israel, Durham NC)) with advanced thermal stimulator (ATS) will be used to apply 6 thermal stimuli to participants' left volar forearm, 5cm from the wrist. The thermal baseline temperature will be set to 32°C. The Medoc system order of stimuli (3 cold and 3 warm) with a rest period between stimuli.

At the start of each trial, the thermode increases or decreases in temperature at the rate of 1°C per second and participants are instructed to push a button when the stimuli is considered painful. After participants press the button, the thermode returns to baseline temperature and the next trial begins. The participants are also given a separate shut off button which terminates the testing.

The second part of the test (summation) will include a single stimulus with the thermode set at 5°C with a 45 second timed stimulus. Subjects will use a verbal rating scale (VRS) to rate the painfulness of the stimulus at 10 second intervals (anchored with “no pain” 0 and 100 “worst pain imaginable”)

Phases III and IV will rely on the collection of patient data using a brief questionnaire and surveys at 6 weeks and 3 months postpartum.

Phases V and VI will rely on perineal pain score (VRS) responses at 6 and 12 months post-delivery.

A pre-survey notification message (via phone or email) will be sent to patients prior to phases III and IV. A personalized cover letter will be included with the surveys. Non-respondents will be contacted using combination of messages and surveys.

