#### **WITHDRAWAL OF PARTICIPANTS:**

A subject can request withdrawal from the study at any time. A clinical research team member will contact the PI by secured-email to inform her about the event that led to early study termination. No further research procedures will be performed, and if the subject additionally requests, all data to that point will not be used.

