**Ketamine:**

Most Frequent: delirium, hallucinations, mood changes, nightmares, tachyarrhythmia, tonic-clonic epilepsy, vocalization

Less Frequent: bradycardia, hypertension, respiratory depression, vomiting, increased intraocular pressure, flashbacks several weeks post operatively

Rare: anaphylaxis, anorexia, diplopia, injection site irritation, laryngismus, nausea, nystagmus, obstructive pulmonary disease, skin inflammation, skin rash

These side effects are uncommon with the lower dose range used in this study.

The risk of the use of the Pathway Pain & sensory evaluation system (Medoc, Dunham, NC) include slight redness on the skin from securing the sensor to the arm with velcro.

There is the risk of the subject becoming emotionally uncomfortable answering some of the surveys' or questionnaires.

Participants are at risk for loss of confidentiality. Strict measures will be in place to ensure that no loss of confidentiality occurs. All participants will be assigned a participant study number that will be used to identify them. One document will link the participant name to their participant number, and this will be kept in a password-protected computer in a locked office in the Prentice Women's Hospital. Only study team members will have access to the study data.

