The Asher Center for the Study and Treatment of Depressive Disorders, directed by [name] MS, is a clinical research women's mental health program at Northwestern's Department of Psychiatry and Behavioral Sciences. [name] holds academic appointments in the Departments of Psychiatry and Behavioral Sciences and Obstetrics and Gynecology. The Asher Center includes 10,000 square feet of research space which accommodates investigators and staff performing and mental health evaluations and research. This space is integrated with a 5,000 square foot clinical care program staffed by an interdisciplinary team of psychiatrists, psychologists, a maternal-fetal medicine research scholar, nurses, and trainees. The Asher Center is located one block from Prentice Women's Hospital. The Asher Center includes two examination rooms specifically furnished with space for examination of mothers and infants, with digital weight scales accurate to .01 g. Two conference rooms (for 12 or 30 people) with audiovisual equipment are available for staff meetings and for other work-related functions. The family room includes comfortable sofas, rocking chairs, and toys for children of all ages. The Center has diaper changes and waste containers in all restrooms. Quiet rooms for breastfeeding women and a kitchen with sink, refrigerator, microwave and snacks are also available.

[name] and Asher Center staff will provide consultation regarding use of the depression assessments and interpretation of depression measures and data, as well as participate in manuscript development. Our resources will be utilized for emergent psychiatric situations that may arise, such as suicidality.

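### Board safety review is required only every 50 subjects or after a rapid response event, so a serious adverse event after discharge need not reach the board until the next count

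*Combined protocol and SAP*

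**What the plan says.** **Board review.** Under Provisions to Monitor the Data to Ensure the Safety of Participants, a board meets with the study research personnel, using the medical record and the data collection form. The timing rule is "It will be reviewed every 50 subjects or if one of the study subject experiences a rapid response team intervention and review". The section does not say at what point a subject is counted, and it gives no stopping rule.

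**Other event reporting.** Under Withdrawal of Participants, "A clinical research team member will contact the PI by secured-email to inform her about the event that led to early study termination". That message goes to the principal investigator, and only for an event that ends participation. No section defines a serious adverse event or sets a reporting time for one.

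**Late harms that the protocol foresees.** The ketamine risk list includes mood changes and "flashbacks several weeks post operatively", with the remark that the listed effects are uncommon at this dose. Resources Available says of the depression centre, "Our resources will be utilized for emergent psychiatric situations that may arise, such as suicidality". Its staff also "will provide consultation regarding use of the depression assessments and interpretation of depression measures and data".

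**Follow-up.** Study Timelines plans about one year of enrolment and follow-up to 12 months postpartum. In the Study timeline table, the 6-week and 3-month rounds, both with the Edinburgh depression scale (EPDS), carry the note "Information will be collected remotely via electronic and/or printed surveys, depending on the patient's preference".

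**The concern.** Both interventions are given once, before or as the epidural catheter comes out. Board review can therefore protect only women who have not yet been dosed, and its value depends on how soon it follows a signal.

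The only early trigger is tied to a hospital response system. The harms that the protocol expects after discharge (suicidality, mood change, flashbacks weeks later) would ordinarily occur where no rapid response team is called. A woman admitted to a psychiatric unit at 6 weeks would meet neither condition for review unless a count of 50 happened to fall due. Meanwhile enrolment continues, with four in five new women receiving morphine and two in five also receiving ketamine.

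**Working it through.** The plan states no figure for this delay, so there is none to reproduce. The check has two parts.

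**1. Is there any other route to the board?** Reading the sections side by side:
- Safety monitoring: every 50 subjects, or a rapid response.
- Withdrawal of Participants: to the investigator only, and only for an event leading to withdrawal.
- Resources Available: clinical management and advice on the depression measures, with no stated report to the board.
- Procedures Involved, on the remote surveys: pre-survey notices, a cover letter, and "Non-respondents will be contacted using combination of messages and surveys". Nothing concerns the content of an answer.

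No other section adds a trigger.

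**2. How many women could be dosed before the next required review?**

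Inputs from the protocol:
- 150 women in the sample size calculation, with recruitment up to 160.
- Enrolment over about one year.
- Allocation: "The subjects will be randomized to a 1/5 chance for group 1 and a 2/5 chance for group 2 and group 3".
- Review at counts of 50, 100 and 150.

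Assumptions: even accrual over 365 days, no losses, and one modelled event per woman at each of 42 days (6 weeks) and 91 days (3 months).

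Formulas, with a = 365/N days between women:
- Woman i is dosed on day i·a, and her event falls on day i·a + d, with d = 42 or 91.
- Review k falls on day 50k·a if subjects are counted at enrolment, or 50k·a + 91 if counted at the 3-month form.
- Women exposed during the delay are those dosed after the event and up to the next review.

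Waits and women dosed in the table cover only events that have a later review.

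| Counted at | N | Review days | Events after last review | Mean wait (max), days | Mean further women dosed (max) |
|---|---|---|---|---|---|
| Enrolment | 150 | 122, 243, 365 | 56 of 300 | 56.1 (121) | 23.4 (50) |
| Enrolment | 160 | 114, 228, 342 | 79 of 320 | 52.1 (113) | 23.4 (50) |
| 3-month form | 150 | 213, 334, 456 | 0 of 300 | 67.9 (168) | 24.8 for 6-week events, 16.9 for 3-month events (69) |
| 3-month form | 160 | 205, 319, 433 | 10 of 320 | 63.5 (161) | 24.5 for 6-week events, 17.7 for 3-month events (70) |

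**Maximum, enrolment count.** An event just after one count is followed by 50 more women before the next, whatever the accrual speed. Of these, 50 × 4/5 = 40 receive morphine, and 50 × 2/5 = 20 receive ketamine as well.

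**Maximum, 3-month-form count, N = 160.** The first woman is dosed on day 2.3, and her 6-week event falls on day 44.3. The first review is on day 114.1 + 91 = 205.1. The wait is 160.8 days, and 160.8/2.28 gives 70 women. This bound does depend on accrual speed.

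**Mean over all modelled events, enrolment count.** The 23.4 leaves out events after the last review.
- N = 150: no one is undosed after the last review, so the mean is 23.4 × 244/300 = 19.0.
- N = 160: 23.4 × 241/320 = 17.6. Counting the last 10 women, who are dosed after the 150-subject review, brings it to about 18.

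The ketamine share of 18 to 19 women is 18 × 2/5 to 19 × 2/5, about 7 to 8. Among events before the last review it is 23.4 × 2/5, about 9.

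**The case against.** The strongest reply is that the practical gap is smaller than the wording suggests.
- Study personnel sit with the board and also collect the follow-up, so someone present may know of an event.
- Review draws on the medical record, not only on survey forms.
- Nothing forbids an earlier meeting.
- The listed ketamine effects are described as uncommon at this dose.
- With no stopping rule, nothing shows that an earlier meeting over one event would change dosing.

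All of this stands, and it limits the weight of the point. It does not supply a trigger: informal knowledge of an event does not oblige the board to review it.

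Three stronger readings are tempting, and the documents do not support them.
- *A reader might infer that a woman in a psychiatric crisis would go without care.* The depression centre's resources are committed to exactly that situation.
- *A reader might take 50 or 70 as a number of women harmed.* They are the most who could be dosed during a delay. No event rate is given, so no number affected can be derived.
- *A reader might infer that depression answers go unread.* The documents are silent on when the remote forms are scored. Consent pages are not among the material reviewed, so instructions to participants may exist there. The first EPDS round is planned in person at the perineal clinic, although the inclusion criteria also allow follow-up at the obstetrician's office, and the thermal test is conditional on clinic attendance.

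**Conclusion.** The concern holds as a gap in board escalation. The review rule is too narrow for a trial with 12 months of follow-up and foreseen psychiatric events after discharge.

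The size depends on a counting rule that the protocol leaves open: at most 50 further women dosed if subjects are counted at enrolment, and about 70 if counted at the 3-month form. The average is more modest. On the enrolment count it is 18 to 19 women per modelled late event, or 23 to 24 if only events before the last review are considered. All but the bound of 50 rest on even one-year accrual, and the averages also on events at 6 weeks or 3 months.

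The rule should be changed because the change is cheap and protects women not yet dosed. Confidence is medium, since earlier review is permitted but not required.

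**What to change.** Amend the timing sentence in the safety monitoring section, for example:

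> Safety data will be reviewed at each 50 subjects enrolled, and promptly after any serious adverse event at any time in follow-up, including suicidality, psychiatric admission or a rapid response team intervention. Such reviews stay blinded unless care requires the code.

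The blinding clause matters because study personnel sit with the board. The cost is one sentence and a few unscheduled reviews, some of them for events unrelated to study drug.

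A separate and secondary point concerns care of women already dosed. Score the remote 6-week and 3-month EPDS on receipt, and refer positive self-harm answers to a study physician and the depression centre. This costs one sentence and a survey alert. A positive EPDS alone should not trigger board review.

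A closing review after the last 3-month form is optional. It would complete the safety record but would come too late to protect undosed women.
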